#### SMQ terms defining a cardiovascular event

- Cardiac arrhythmias
- Cardiac Failure
- Cardiomyopathy
- Central nervous system haemorrhages and cerebrovascular conditions (*Stroke*; including sub-SMQs hemorrhagic and ischemic cerebrovascular conditions, and conditions associated with CNS hemorrhages and cerebrovascular accidents)
- Embolic and thrombotic events (including sub-SMQs arterial, venous, and unspecified/mixed)
- Ischemic heart disease (*Coronary artery disease*; including sub-SMQs myocardial infarction and other ischemic heart disease)
- Torsade de pointes/QT prolongation

#### SMQ term defining new onset diabetes mellitus

- Hyperglycaemia/new onset diabetes mellitus

#### SMQ term defining worsening of osteoporosis or osteopenia

- Osteoporosis/osteopenia (for incidence of new onset or worsening)

#### **SMQ term for osteonecrosis (bone fracture event)**

- Osteonecrosis

Complete lists of SMQ terms and codes are found in Appendix 4.

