## 2 Study Objectives and Endpoints

### 2.1 Objectives

#### Primary Objective

The primary objective of this observational study is to describe the risk of the following Adverse Event of Special Interest (AESI) in association with Firmagon treatment:

- Cardiovascular events
- Events related to decreased bone density, including new onset or progression of osteoporosis or osteopenia, and fractures
- New onset or exacerbation of glucose intolerance or type 2 diabetes mellitus
- Changes in hepatic enzyme levels

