### 2.2 Endpoints

#### Safety Endpoints

The following endpoints will be analysed in the study:

1. Rate of AESI
  - a. Incidence rate of cardiovascular events
  - b. Incidence rate of bone fracture, including osteoporotic/fragility fractures
  - c. Incidence rate of new onset or worsening osteoporosis or osteopenia

- d. Incidence rate of new-onset diabetes mellitus
  - e. Incidence rate of all-cause mortality
2. Occurrence of relevant laboratory value changes
- a. Changes in hepatic enzymes, fasting serum glucose, testosterone and PSA levels
  - b. Incidence rate of glucose intolerance

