### 3.2 Study Sample Size

In a pivotal one-year Phase 3 study (Ferring Clinical Study FE200486 CS21), a serious cardiovascular event rate for Firmagon of 5 per 100 patient-years was observed in the sub-group of patients with locally advanced or metastatic PCa. In the same study, in patients treated with the GnRH agonist (leuprolide) a serious cardiovascular event rate of 8 per 100 patient-years was observed. Based on SEER database in over 22,000 PCa patients treated with GnRH agonists the expected incidence rate is approximately 10 per 100 patient years [1]. In an observational study of 73,000 Medicare enrollees with locoregional PCa, Keating et al. [2] found incidence rates of 7.23, 1.29, and 1.35 respectively for coronary heart disease, sudden cardiac death, and myocardial infarction in patients treated with GnRH agonists. Keating et al additionally showed an incident rate for new onset diabetes of 2.90 in GnRH agonist treated patients.

In the CS21 study, a bone fracture rate of 0.6 per 100 patient years for patients treated with Firmagon vs. 2.2 per 100 patient years for patients treated with leuprolide was observed in the sub-group of patients with locally advanced or metastatic PCa. However, CS21 was a one-year study, and annual fracture rates increase with age and also with an increased number of doses of GnRH agonist [3]. Therefore, the incidence rates in a longer-term observational study are anticipated to be higher. Smith et al [4] report a fracture rate of 7.91 per 100 person-years in 3,779 men with PCa (all stages) who received GnRH agonist treatment during a 5-year observation period.

With the expected incidence rates for cardiovascular events, diabetes and fracture as indicated above, 1,000 patients on Firmagon, and 500 on GnRH agonist treatment for a 5-year follow-up study and assuming a dropout rate of 10% over the course of 5 years, and a uniform distribution for the time to dropout, the 95% confidence interval for estimating the incidence rates are listed in Table 2 below (please note that the confidence interval for the smaller comparator group will be wider). These confidence intervals show the precision for estimating the incidence rates if the observed incidence rates are the same as reported in literature. The width of the 95% confidence interval is also listed in the table. The calculation was performed in STATA 11 (College Station, TX).

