**Table 2 Incidence Rates for Cardiovascular Events and Fracture Reported in Literature, and the 95% Confidence Intervals the Study is Anticipated to Obtain Based on 1000 Patients on Firmagon and a Follow-up of 5 Years.**

Event	Source	Incidence rate (per 100 patient years on Firmagon)	95% Confidence Interval	Width of the 95% confidence interval
Cardiovascular events	SEER data	10.00*	9.14, 10.91	1.77
	CS21	5.00	4.38, 5.68	1.30
Coronary heart disease	Keating et al.	7.23*	6.48, 8.02	1.54
Sudden cardiac death	Keating et al.	1.29*	0.98, 1.66	0.68
Myocardial infarction	Keating et al.	1.35*	1.04, 1.74	0.70
Fractures	Smith et al.	7.91*	7.14, 8.74	1.60
	CS21	0.60	0.40, 0.87	0.47
New-onset diabetes	Keating et al.	2.90*	2.44, 3.45	1.01

\*Incidence rate for GnRH agonist, assumed to be same with Firmagon

Based on the estimates and 95% Confidence Intervals widths described above, the planned sample size (with 1000 patients enrolled on Firmagon) is considered sufficient to address the objectives of this Observational study, with reasonable precision.

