### 10.4.1 Definition

The main objective of this observational study is to collect information on AESI. Specifically: cardiovascular events; new onset of diabetes mellitus; progression of osteoporosis or osteopenia; events associated with bone fractures (osteonecrosis); and all-cause mortality. The worsening of glucose intolerance based on lab data has been described in Section 9.1.5. Only events classified as serious will be considered.

Any AESI in the medical history occurring during the “Main Treatment Period” (or thereafter), or any adverse event of special interest in the adverse event report log occurring during the “Pre-consent Period” will be listed, as these possibly should be shifted from medical history to adverse event (or opposite).

In order to limit bias from different treatment effects and overlapping treatment periods and to make data comparable to a greater degree *only* AEs reported during the “Main Treatment Period” are considered (see Section 8.1 for details).

The AEs will be coded using MedDRA lowest level term (LLT). An AE included in any of the following Standardised MedDRA queries (SMQs), at the narrow search scope level, is defined as an event of special interest:

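### The bone fracture endpoint is coded only by the Osteonecrosis SMQ, so its planned analyses estimate osteonecrosis, not fracture

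*SAP*

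**What the plan says.** Section 2.1 lists among the primary safety concerns "Events related to decreased bone density, including new onset or progression of osteoporosis or osteopenia, and fractures". Section 2.2 makes endpoint 1b the "Incidence rate of bone fracture, including osteoporotic/fragility fractures".

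The sample size case in Section 3.2 uses fracture rates. From the one-year Phase 3 study it takes "a bone fracture rate of 0.6 per 100 patient years for patients treated with Firmagon", and from a published cohort of GnRH agonist users it takes 7.91 per 100 person-years. Both reappear in Table 2, titled in part "Incidence Rates for Cardiovascular Events and Fracture Reported in Literature".

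The operational definition is in Section 10.4.1. It refers to "events associated with bone fractures (osteonecrosis" in its list of events, and states that an adverse event in one of the listed SMQs, "at the narrow search scope level, is defined as an event of special interest". The entry for this endpoint is headed "SMQ term for osteonecrosis (bone fracture event" and contains Osteonecrosis alone. Section 12 restates that mapping, and Appendix 4 gives its single code, 20000180.

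**The concern.** An endpoint in a safety study is whatever its coded definition collects. Here the objective, the endpoint and the precision table are about fracture, while the code list is about osteonecrosis, a different condition. No SMQ or term list named for fracture appears in Section 10.4.1, Section 12 or Appendix 4.

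The result would also be mislabelled. Section 10.4.3 calls the overview table bone fracture, Appendix 4 heads the code with fractures, and Section 10.5.1 calls the modelled event osteonecrosis. Under the interpretation rule in Section 10.5.1, a confidence interval for the rate ratio that includes 1 is read as failure to establish a difference. An inconclusive osteonecrosis result could then be read as an inconclusive fracture result, in a post-authorisation safety study whose primary objective names fractures.

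**Working it through.** **1. Trace the endpoint through the SAP.**

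| Place in SAP | Event named or used |
|---|---|
| 2.1, primary objective | Fracture |
| 2.2, endpoint 1b | Fracture, with osteoporotic and fragility fractures included |
| 3.2, Table 2 | Fracture (2 of 8 rows); osteonecrosis (0 of 8) |
| 7.6.1, fracture history table | SMQ codes of Appendix 4, broad scope |
| 10.4.1, definition | Osteonecrosis SMQ, narrow scope |
| 10.4.3, overview table | Labelled bone fracture; content follows 10.4.1 |
| 10.5.1, Poisson model | Osteonecrosis |
| 10.5.2 and 10.5.3, Kaplan-Meier and Cox | First event of special interest, as defined in 10.4.1 |
| 12 and Appendix 4 | Osteonecrosis SMQ, with a fracture label |

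Only the Poisson model names osteonecrosis directly. That the time-to-event analyses follow the same definition is an inference: Section 10.4.2 counts the first event within each class, and Section 10.5.3 takes its adjusting factors from the separate models of Section 10.5.1. Even if Section 10.5.2 were read as pooling all classes, fractures would enter only through terms that happen to sit in the listed SMQs.

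**2. Reproduce the plan's own precision figures.** Inputs from Section 3.2: 1,000 Firmagon patients, 5 years, 10% dropout with uniform dropout times.

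Patient-years = 900 × 5 + 100 × 2.5 = 4,750.

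Expected events = rate per 100 patient-years × 47.50, with an exact Poisson (chi-square) 95% interval divided by 47.50:

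| Rate per 100 PY | Expected events | Recomputed 95% CI (width) | Table 2 |
|---|---|---|---|
| 0.60 | 0.60 × 47.50 = 28.5 | 0.40 to 0.86 (0.46) | 0.40 to 0.87 (0.47) |
| 7.91 | 7.91 × 47.50 = 375.7 | 7.13 to 8.75 (1.62) | 7.14 to 8.74 (1.60) |

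The agreement is within about 3%. Table 2's arithmetic is sound, and its precision is precision for fractures.

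**3. Try the same for the endpoint as coded.** This needs an osteonecrosis rate. The SAP gives none, so the expected count and interval width for endpoint 1b as coded cannot be derived.

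**The case against.** - **The mapping is disclosed.** Section 12 sets the protocol's fracture endpoint beside the Osteonecrosis SMQ, and the protocol, which is not at hand, may explain the choice. That is fair on transparency, but the SAP gives no reason, and disclosure does not make the query measure fracture.
- **The SMQ contents are not shown.** Section 10.4.1 promises complete term lists, but Appendix 4 gives only SMQ names and codes. The share of fractures lost therefore cannot be stated. This limits the size of the finding, not its direction. If the Osteoporosis/osteopenia SMQ holds fracture terms, those events would count under endpoint 1c, not 1b.
- **Fractures are reported elsewhere.** This is the strongest point. The general adverse event tables (Sections 10.1.1 and 10.3.2) show fractures by preferred term with crude rates, confidence intervals and a between-group test. However, they give no pooled fracture rate, no adjusted ratio and no time-to-event analysis, and they cover a different window: Section 10.2 includes events after the Main Treatment Period, which Section 10.4.1 excludes for events of special interest.
- **T-score tables.** The most severe category in Table 3 requires an osteoporotic fracture and is tabulated by visit (Section 10.8.3), but only for patients with a T-score. It is not an incidence rate.

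The loose labelling in Section 10.4.3 affects other endpoints too, so it is weak evidence on its own. The mapping in Sections 10.4.1, 10.5.1, 12 and Appendix 4 does not depend on it.

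**Conclusion.** The concern holds and must be fixed before analysis. A named component of the primary objective, and of the secondary between-group comparison, has no pooled or adjusted analysis that measures it, and the analysis put in its place carries its label.

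In size, the two fracture rows of Table 2 (about 28 and 376 expected Firmagon events) do not apply to the endpoint as coded, and nothing in the SAP supports its precision. The conclusion rests on two premises: that osteonecrosis and fracture are distinct events, and that the Osteonecrosis SMQ collects what its name says. The event counts rest on the rates and dropout stated in Section 3.2. No osteonecrosis rate and no proportion of missed fractures is assumed.

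**What to change.** 1. Define endpoint 1b by a pre-specified MedDRA fracture term list, identifying osteoporotic and fragility fractures as far as the coded terms allow. Fix the list before the data are analysed.
2. Use it in Sections 7.6.1, 10.4.1, 10.4.3, 10.5.1 to 10.5.3, 12 and Appendix 4.
3. Report osteonecrosis separately, under its own name.
4. State whether fracture terms within the Osteoporosis/osteopenia SMQ count under endpoint 1b, 1c or both.

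A separate point arises in the same text. Section 10.4.1 says "Only events classified as serious will be considered", while the overview table in Section 10.4.3 has distinct rows for all and for serious events, which would be redundant under that rule. Reconcile the two. If the restriction applies to fractures, state that Table 2's fracture precision does not carry it.

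The cost is SAP wording and one term list. Section 10.4.1 already codes adverse events to MedDRA lowest level term, and Section 10.3 reports all of them, so an all-fracture list needs no new data. The SAP does not show whether fracture mechanism is recorded, so the fragility subset is limited to what coded terms reveal.

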### **10.4.2 Incidence of Adverse Events of Special Interest**

A summary table will be prepared for the incidence of each AESI. For example, for cardiovascular events, the first AE in the class of the CV SMQs will be accounted for, while the other events will be disregarded. For the incidence rate, it will be the time to this event that is used. Should no event occur, patient is lost to follow-up, or completes the trial (without an event) it is the total observed exposure time that is used, while the patient does not contribute to the derived endpoint count.

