## 8 Exposure

One of the objectives in the study is to collect AESIs and compare long-term clinical experience with specific important conditions between Firmagon and agonist therapies. The therapy regimens may change, e.g. from continuous treatment to intermittent, at the discretion of the investigator. This section defines exposure periods that are used in order to be able to make unbiased (continuous) treatment comparisons of treatment-emergent adverse events.

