### 8.1 Exposure Periods

In order to limit bias from different treatment effects and overlapping treatment periods on reported adverse events, and to make data comparable to a greater degree, the total exposure period will be partitioned as follows.

At the Baseline Visit patients will be asked if they are on ADT and if so, when it was initiated. The date of Informed Consent is also recorded as part of the eCRF data collection. Start date of *main treatment period* will be considered to be the date at which both the informed consent has been signed, and the first dose has been administered. End date of main treatment period will be recorded as date of loss to follow-up, change in ADT, discontinuation of ADT, or end-of-trial visit, whatever comes first. If treatment continues after end of main treatment period (e.g. due to regimen change), a consecutive treatment period will be considered to be started. Consecutive treatment periods have a similar definition of end-of treatment period as the main treatment period.

In the case that the informed consent was not signed at time of first dosing, a “pre-consent period” is considered. This period ends when the informed consent is signed, at which time the “Main Treatment Period” starts, see Table 4.

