## **8.2 Extent of Exposure**

The extent of exposure (in months of treatment (and in mg)) from start of “Main Treatment Period” to end of last period will be summarised by treatment and presented by descriptive statistics.

Similarly, the extent of exposure (in months of treatment (and in mg)) from start of “Main Treatment Period” to end of “Main Treatment Period” will be summarised by treatment and presented by descriptive statistics. A similar table of the extent of exposure during the “Pre-treatment Period” will be supplied.

Number of subjects in the different periods will be summarized, with percentages relative to the number of subjects in the “Main Treatment Period”.

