## 10.5 Analyses of Adverse Events of Special Interest

### 10.5.1 Primary Analysis of Adverse Events of Special Interest (AESI)

The mortality rate and respective incidence rates (number of AEs per 100 person years) of each AESI will be estimated using a Poisson regression model. In general, assuming a constant incidence rate of  $\lambda_{i,j}$  per unit time for a category  $i$ , treatment  $j$  ( $=0$  for GnRH agonist and 1 for Firmagon), the number of events  $y_{i,j}$  observed during a time interval of length  $t_{i,j}$  (unit 100 years) is distributed as Poisson with mean  $\mu_{i,j}=\lambda_{i,j}t_{i,j}$ . The mean of a Poisson distributed variable is modelled by

$$\log \mu_{i,j} = \log \lambda_{i,j} - \log t_{i,j} = \alpha + \beta_j + \beta_{i,j} x_{i,j},$$

where  $t_{i,j}$  is the number of person years, and  $\log(t_{i,j})$  is modelled as the “offset” with regression coefficient equal to one. Besides the effects of intercept ( $\alpha$ ) and treatment, modelled by  $\beta_j$  (with GnRH agonist as reference; e.g.  $\beta_0=0$ ), the incidence rate (mean) is driven by the adjusting factors for the present category. By this, the adjusted incidence rate ratio (IRR) of an incidence for patients on Firmagon as compared to GnRH agonist is estimated by  $\exp(\beta_i)$ . For more details, please see page 501 of [5], and page 204 of [6].

Table 5 illustrates data from one treatment arm by each category of adjusting factors (age and stage of disease) used in the model. This example may be extended to include more adjusting factors if required.

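### AESIs count only in the Main Treatment Period, but their person-time and censoring are not tied to that period, and the window for all-cause mortality is not stated

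*SAP*

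**What the plan says.** **Events.** SAP 10.4.1 limits AESIs by window: only "AEs reported during the “Main Treatment Period” are considered". Under 8.1 the main period ends at "date of loss to follow-up, change in ADT, discontinuation of ADT, or end-of-trial visit, whatever comes first". If treatment goes on after that, for instance after a regimen change, "a consecutive treatment period will be considered to be started".

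**Person-time.** Under 10.4.2 a patient with an event contributes time to the first event. For a patient without one, "it is the total observed exposure time that is used". The circumstances named there are no event, loss to follow-up and completion of the trial; the end of the main period is not named.

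**What total exposure means elsewhere.** In 8.1, "the total exposure period will be partitioned as follows", and the parts are the pre-consent, main and later periods. In 8.2, exposure "from start of “Main Treatment Period” to end of last period" is reported separately from exposure within the main period.

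**Models.** In 10.5.1 the offset variable "is the number of person years, and" has no period attached. 10.5.2 says that patients lost to follow-up are censored. 10.5.3 lists adjustment factors and gives no risk period.

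**Mortality.** 2.2 makes all-cause mortality an endpoint, and 10.4.1 lists it among the AESIs. 10.6 remarks that death is not itself an adverse event. 8.1 does not list death as an end of the main period, and 3.1 continues safety follow-up after ADT stops.

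**The concern.** A rate needs one window for its events and its person-time. Here the numerator has an explicit window and the denominator has a phrase that, in the SAP's own vocabulary, points to a longer one. A patient who changes ADT in year 2 and stays on treatment to year 5 could add three years to the denominator, and stay in the Kaplan-Meier and Cox risk sets, while no AESI in those years can count.

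The affected results are the primary Poisson rates and incidence rate ratios (IRRs) of 10.5.1. The primary objective is descriptive, so a rate that is too low matters even when the ratio is right. Two programmers could each follow the SAP and report different primary rates.

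For mortality, deaths in the main period and deaths over all follow-up are different estimands, and the text can be read either way.

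**Working it through.** **1. The plan's own figure.** Inputs from 3.2: 1,000 Firmagon patients, 5 years, 10% dropout spread uniformly. Person-years = 900 × 5 + 100 × 2.5 = 4,750. At 5.00 per 100 patient-years that is 237.5 events, and the exact Poisson 95% interval is 4.38-5.68, as printed in Table 2. At 10.00 it is 9.12-10.94, against 9.14-10.91 printed. So Table 2 is consistent with full follow-up less dropout. It has no stop at first event or ADT change. As precision planning, it does not settle the analysis window.

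**2. Effect of a longer denominator.** Let f be the share of counted person-time outside the main period. Then

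- reported rate = true main-period rate × (1 - f)
- reported IRR = true IRR × (1 - f_F)/(1 - f_A), with F for Firmagon and A for agonist.

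**3. Size of f.** The SAP gives none, so these inputs are assumed: constant AESI rate L, ADT change rate c per year, share s of the time after a change that is on treatment, dropout survival 1 - 0.02t as in 3.2, deaths not modelled. Per 1,000 patients, integrating t from 0 to 5:

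- main = 1000 ∫ exp(-(L+c)t)(1 - 0.02t) dt
- later = 1000 ∫ [c/(L+c)][1 - exp(-(L+c)t)](1 - 0.02t) dt
- f = s × later / (main + s × later)

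For L = 0.05, that is 5.0 per 100 patient-years:

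| c per year | main PY | later PY | f (rate), s = 25% | s = 50% | s = 100% |
|---|---|---|---|---|---|
| 2.5% | 3,974 | 259 | 1.6% (4.92) | 3.2% (4.84) | 6.1% (4.69) |
| 5% | 3,754 | 498 | 3.2% (4.84) | 6.2% (4.69) | 11.7% (4.41) |
| 10% | 3,363 | 924 | 6.4% (4.68) | 12.1% (4.40) | 21.6% (3.92) |

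Corner cells: 0.25 × 259/(3,974 + 65) = 0.016, and 924/(3,363 + 924) = 0.216.

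For L = 0.10 with s = 50%: c = 5% gives 231/(3,363 + 231) = 6.4% and a rate of 9.36; c = 10% gives 430/(3,028 + 430) = 12.4% and a rate of 8.76, below the Table 2 interval.

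**4. IRR.** With equal c and s in both arms, f is essentially equal and cancels. If one arm changes at 10% and the other at 5% per year (assumed, L = 0.05, s = 50%), a true IRR of 1 becomes 0.879/0.938 = 0.94, or 1.07 the other way round.

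**5. Kaplan-Meier.** If patients still treated after a change stay in the risk set, the apparent hazard at time t is L × main(t)/(main(t) + s × later(t)), where main(t) and later(t) are the integrands above. With L = 0.05 and s = 50%, five-year 1-KM is 20.8% (c = 5%) or 19.5% (c = 10%), against a true 1 - exp(-0.25) = 22.1%.

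**6. Pre-consent time.** Read fully literally, the whole that 8.1 partitions also includes exposure before consent. No figure is attempted, because nothing in the SAP gives its length.

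**The case against.** The strongest reply is that 10.4.2 follows directly on the rule limiting AESIs to the main period, and that Section 8 defines the periods "in order to be able to make unbiased (continuous) treatment comparisons of treatment-emergent adverse events". On that reading, total merely contrasts with time to first event, and exposure time means main-period time. Two of the four events that end the main period, loss to follow-up and the end-of-trial visit, correspond to circumstances that 10.4.2 names. This is a fair reading, and under it the bias is zero. What remains is that 10.4.2 does not say so, while 8.1 and 8.2 use total and all-period exposure for something longer.

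A reader might infer stronger points that the text does not support:

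- **That all follow-up time, including time off ADT, enters the denominator.** 10.4.2 speaks of exposure time, so only treated time is at issue.
- **That 10.5.2 censors only at loss to follow-up.** It does not say only, and an exhaustive reading would leave event-free completers uncensored. 10.5.2 and 10.5.3 are silent on the main period; they do not state a wrong rule.
- **That the comparison is tilted towards one drug.** This needs unequal ADT change rates, and the SAP gives none.
- **That the treatment-emergence rules in 10.2 and 10.3 conflict.** The 45-day rule in 10.3 is a special case for patients without an end-of-trial visit. It narrows 10.2 and does not set the AESI window.

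On mortality, its place in the AESI list supports the main period as the default, and the remark that death is not an adverse event stands in the exploratory section. These points favour one reading without settling it.

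**Conclusion.** The concern holds as a missing tie between the event window and the person-time of the primary analysis. It does not show that the programmed denominator will be wrong. Restricting AESIs to the main period is deliberate and is not questioned.

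If 10.4.2 is applied in the vocabulary of 8.1 and 8.2, the primary rates are biased low. The loss is 1.6-21.6% for a true 5.0 per 100 patient-years; the low end of the reported range, 3.92, lies below the Table 2 interval. These sizes rest wholly on the assumed ADT change rates and on-treatment shares.

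The mortality window is a second, separate gap. No size is given for it, because the SAP offers nothing from which to derive one. Both should be settled before results are seen.

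**What to change.** **AESIs.** In 10.4.2, replace the total-exposure wording with time from the start of the Main Treatment Period to the earliest of first event, death or end of that period. State that the same person-time is the offset in 10.5.1 and that 10.5.2 and 10.5.3 censor at the same point. List death in 8.1 as an end of the period.

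**Mortality.** State one window in which deaths and person-time start and end at the same points. State one attribution rule for deaths and person-time after a switch between drug classes, with the alternative as a sensitivity analysis. The choice is the sponsor's. Section 6 calls for analysis by treatment received, but does not say which class owns a death after a switch.

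**Cost.** SAP wording and minor programming, with no new data. The intervals will be wider than in Table 2. For a 5.0 rate in 1,000 Firmagon patients, before any allowance for death:

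| Person-time rule | PY | Expected events | Exact 95% CI width |
|---|---|---|---|
| Table 2 | 4,750 | 237.5 | 1.30 (as printed) |
| Stop at first event | 4,212 | 210.6 | 1.38 |
| Also stop at ADT change, 5% per year (assumed) | 3,754 | 187.7 | 1.46 |
| Also stop at ADT change, 10% per year (assumed) | 3,363 | 168.2 | 1.54 |

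The step from 1.30 to 1.38 follows from counting first events, which 10.4.2 already does.
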